3.3.2.4 Adverse Events (AEs)

Documentation of AEs will be recorded in the eCRF from the time informed consent is provided until time of screen failure, time subject is withdrawn from study, time of hospital discharge, death, or until 4 weeks after the last dose of study drug, whichever comes first. All AEs should be followed until either resolution (or return to normal or Baseline values), until judged by the Investigator to no longer be clinically significant or until 4 weeks after last dose of study drug. Subjects with ongoing AEs at the time of hospital discharge will continue to be followed for their AEs until either resolution (or return to normal or Baseline values), until judged by the Investigator to no longer be clinically significant, or until 4 weeks after last dose of study drug. All SAEs will be followed until resolution, death, or the subject is lost to follow-up, even if they are ongoing more than 4 weeks after the last dose of study drug. Sections [9](#) and [15.1](#) provide the definitions and guidelines for recording AEs. If the subject receives Remodulin after hospital discharge, beyond Day 56/End of study, or following withdrawal from the study, AEs/SAEs will be subject to AE/SAE reporting under local government post-marketing AE/SAE reporting requirements.

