3.6 ESTIMATED STUDY DURATION

No subject will receive study drug for greater than 28 days (4 weeks). Post-treatment data will be collected until death, time of hospital discharge, time of study withdrawal, or until 4 weeks after last dose of study drug, whichever comes first. Subjects with ongoing AEs at the time of hospital discharge or study withdrawal will be followed for their AEs until either resolution (or return to normal or Baseline values), until judged by the Investigator to no longer be clinically significant, or for up to 4 weeks beyond the subject's last dose of study drug. Therefore, the maximum amount of time a subject randomized to study drug would be in the study is 56 days (a maximum of 28 days of study drug, plus 4 week follow-up (28 days) after last dose/discontinuing study drug). Per the Investigator's discretion, if Remodulin treatment is needed beyond Day 28, subjects will be transitioned to commercial product; Day 28 will be considered as the last day of study drug administration. These subjects will continue to be followed in the study until they have reached Day 56 (4 weeks after last dose of study drug), have been discharged from the hospital or withdrawn from the study, whichever comes first.

The study will be completed once 66 evaluable subjects have been enrolled and completed the last patient last visit/assessment.

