6.2 ACCESS TO BLINDED TREATMENT ASSIGNMENT

In the event of a medical emergency that requires immediate unblinding, an unblinding call may be made to determine treatment assignment. The identity of a subject's treatment assignment, should it need to be obtained, will occur through an unblinding call to the 24 hour [REDACTED]

[REDACTED]. Investigators will be permitted to access the treatment assignment upon the subject meeting the criterion for clinical worsening or after the completion of Day 14 if required for purposes of medically managing the subject (e.g., another prostacyclin will be initiated). Subjects randomized to placebo may be discontinued from study drug at that time. Subjects randomized to Remodulin who have residual or chronic pulmonary hypertension that does not fully resolve by Day 14 may continue to receive study drug for up to an additional 14 days (for a total of up to 28 days) per the Investigator's discretion. Subjects who have PPHN resolved by Day 14, who have already begun weaning by Day 14 or for whom it is anticipated that weaning of study drug will begin within

shortly after completing Day 14, or who are withdrawn from the study should remain blinded. All attempts should be made to maintain the blind during the study.

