7.3.4 Follow-up/End of Study

The following assessments will be conducted during a final assessment visit at the time of withdrawal from the study, hospital discharge, or at 4 weeks after discontinuing study drug, whichever comes first, for all subjects who receive study drug. In the event that a subject randomized to Remodulin will receive commercial Remodulin beyond Day 28, and the subject has not been discharged from the hospital or withdrawn from the study, these assessments should take place on Day 56.

- Physical exam including height and weight
- Vital signs (BP, RR, HR, Temp, SpO₂)
- Clinical laboratory assessments (See Section 3.3.2.3)
- Record AEs

Subjects with ongoing AEs at the time of hospital discharge will continue to be followed for their AEs until either resolution (or return to normal or Baseline values), until judged by the Investigator to no longer be clinically significant, or until 4 weeks after last dose of study drug.

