9.3 PERIOD OF OBSERVATION

For the purposes of this study, the period of observation starts from the time the informed consent is signed and concludes upon meeting screen failure criteria, at the time of death, at the time of hospital discharge, at the time of withdrawal from the study, or at 4 weeks after last dose of study drug, whichever comes first. Day 28 will be considered as the last day of study drug administration for subjects who continue on Remodulin. Subjects with ongoing AEs at the time of hospital discharge will continue to be followed for their AEs until either resolution (or return to normal or Baseline values), until judged by the Investigator to no longer be clinically significant, or until 4 weeks after last dose of study drug. All SAEs should be followed until resolution, death, or the subject is lost to follow-up, even if they are ongoing more than 4 weeks after the last dose of study drug.

If the subject receives commercial Remodulin after hospital discharge, beyond Day 56/End of study, or following withdrawal from the study, AEs/SAEs will be subject to AE/SAE reporting under local government post-marketing AE/SAE reporting requirements.

Supplemental measurements and/or evaluations may be necessary to investigate fully the nature and/or causality of an AE or SAE. This may include additional laboratory tests, diagnostic procedures, or consultation with other healthcare professionals. The eCRF pages should be updated with any new or additional information as appropriate.

If the Investigator detects an SAE in the study subject after the end of the period of observation, and considers the event possibly related to prior study treatment, he or she should contact the Sponsor to determine how the event should be documented and reported.

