12.2 ADVERSE EVENTS

All AEs will be coded to PT and SOC using the latest version of the MedDRA coding dictionary. Treatment-emergent adverse events (TEAEs) are those AEs with onset date equal to or after the start date of the study drug. TEAEs will appear in listings and summaries. Non-treatment-emergent AEs (the AEs occurring after signing the Informed Consent Form (ICF), but before receiving study drug) will be listed, but will not be included in summary tables.

The AE listings will include the AE verbatim term and its corresponding PT and SOC, all eCRF details, and a treatment-emergent indicator flag. The following AE listings will be provided:

- All AEs
- Deaths
- SAEs
- AEs leading to permanent discontinuation of study drug

All AE summaries will be sorted by overall frequency and/or SOC and will include the number and percentage of subjects experiencing each type of AE, the total number of each type of AE, and the AE rate of each type of AE. AE rate will be calculated as the total number of AEs divided by the total patient days of exposure to study drug per treatment group.

The following AE summaries will be provided:

- AEs by SOC and PT
- AEs by PT
- Deaths
- SAEs by SOC and PT
- Non-serious AEs by SOC and PT
- AEs probably or possibly related to study drug by SOC and PT
- AEs leading to permanent discontinuation by PT
- AEs by SOC, PT, and severity (mild, moderate, severe)

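### The AE rate in SAP 12.2 counts adverse events that start off drug but not the days off drug, so it is overstated whenever such events occur

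*SAP*

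**What the plan says.** SAP 12.2 defines the events: "Treatment-emergent adverse events (TEAEs) are those AEs with onset date equal to or after the start date of the study drug". Only AEs that start before the first dose are kept out of the summary tables, and no end of window is given. The rate shown in the AE summaries is then defined: "AE rate will be calculated as the total number of AEs divided by the total patient days of exposure to study drug", by treatment group.

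The protocol sets how long new AEs are recorded. Protocol 3.3.2.4 closes recording at screen failure, withdrawal, discharge, death, "or until 4 weeks after the last dose of study drug, whichever comes first". Protocol 9.3 agrees: apart from screen failure and death, observation ends "at the time of hospital discharge, at the time of withdrawal from the study, or at 4 weeks after last dose of study drug", whichever is earliest.

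Time on drug can depend on the arm. Protocol 6.2 lets the investigator learn the assignment after clinical worsening or after Day 14, if managing the subject requires it. It then says of placebo: "Subjects randomized to placebo may be discontinued from study drug at that time". And of the active arm: "Subjects randomized to Remodulin who have residual or chronic pulmonary hypertension that does not fully resolve by Day 14 may continue", up to 28 days in total.

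For subjects who move to commercial product, Protocol 3.6 says: "Day 28 will be considered as the last day of study drug administration". They are still followed to Day 56 unless they are discharged or withdrawn earlier.

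**The concern.** An exposure-adjusted rate is meant to make arms with different time on drug comparable. That requires events and days to come from the same period. Here an AE that starts after the last dose adds to the numerator, while the days during which it could have started add nothing to the denominator. No other section of either document matches the two.

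Safety is part of the primary objective, and SAP 12.2 puts this rate in every AE summary. A reader could see an arm difference in that column that reflects only how long each arm stayed on drug.

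**Working it through.** **Inputs from the documents.** At most 28 days on study drug and 28 days of follow-up after it (Protocol 3.6). The plan's own maximum time in study reproduces: 28 + 28 = 56 days. The documents give no AE rates, and no mean time on drug or time to discharge by arm, so E, F and h below are assumptions.

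**Formula.** Let r be the on-drug AE hazard per day and hr the off-drug hazard.

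- Expected AEs per subject = rE + hrF
- SAP rate = (rE + hrF)/E = r(1 + hF/E)
- Overstatement relative to the on-drug rate: m = 1 + hF/E

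**Overstatement, and the arm ratio with no true difference** (same F and h in both arms):

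| Case | F | h | hF | m, E=7 | m, E=14 | m, E=28 | Ratio, 28 vs 14 days | Ratio, 7 vs 14 days |
|---|---|---|---|---|---|---|---|---|
| None | 0 | any | 0 | 1.00 | 1.00 | 1.00 | 1.00 | 1.00 |
| Low | 7 | 0.25 | 1.75 | 1.25 | 1.125 | 1.0625 | 0.94 | 1.11 |
| Middle | 14 | 0.5 | 7 | 2.00 | 1.50 | 1.25 | 0.83 | 1.33 |
| Ceiling | 28 | 1 | 28 | 5.00 | 3.00 | 2.00 | 0.67 | 1.67 |

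For example, in the middle case 28 vs 14 days gives 1.25/1.50 = 0.83. If E, F and h are equal in the two arms, the ratio is 1.00 in every row.

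**A separate effect: dilution.** Take E = 14 in both arms, a true on-drug ratio of 1.5 and no difference off drug. The reported ratio is (1.5 × 14 + hF)/(14 + hF):

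- Low: 22.75/15.75 = 1.44
- Middle: 28/21 = 1.33
- Ceiling: 49/42 = 1.17

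The denominators are equal here and cancel. The dilution comes from counting off-drug AEs at all, not from the choice of days. Dividing by all observed days leaves it unchanged; in the ceiling case, (49/42)/(42/42) = 1.17.

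**Test of two possible repairs**, low case (F = 7, h = 0.25), no true difference:

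- *On-drug AEs over on-drug days:* ratio 1.00 for any E, and a true 1.5 is reported as 1.5.
- *All TEAEs over all days from first dose to end of recording:* E=28 gives 29.75/35 = 0.85; E=14 gives 15.75/21 = 0.75; E=7 gives 8.75/14 = 0.625. The ratios are 0.85/0.75 = 1.13 and 0.625/0.75 = 0.83. Both lie further from 1.00 than the SAP rule's 0.94 and 1.11. This rule gives 1.00 only when h = 1 or the split of on and off time is the same in both arms.

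**Effect of a window after last dose.** Suppose, for illustration only, 2 extra days in both numerator and denominator.

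- Low case, 28 vs 14 days: (28.5/30)/(14.5/16) = 1.05. 7 vs 14 days: (7.5/9)/(14.5/16) = 0.92.
- Middle case, 28 vs 14 days: (29/30)/(15/16) = 1.03. 7 vs 14 days: (8/9)/(15/16) = 0.95.

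A short window leaves a small residual; a long one moves towards the second repair.

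**The case against.** The strongest reply is that little depends on this column. Protocol 10.3.3 makes the safety summaries descriptive, centres them on incidence and plans no inferential safety test. Subject counts and percentages sit in the same tables and do not use this denominator. AE onset times and dosing times are collected, so on-drug and off-drug events could be separated from the data. This stands and limits the consequence. It does not repair the rule: a programmer following SAP 12.2 would produce the mismatched rate, and a reader of the summary table would see no on/off split with which to correct it.

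A second reply is that the larger figures are unrealistic. This also stands. Comparing 28 with 14 days treats the longest exposure any subject may have as an arm average. F = 28 with h = 1 assumes that nobody is discharged for four weeks and that AE hazard does not change after stopping. Protocol 6.2 asks that the blind be kept where possible, so arm-dependent stopping reaches only an unblinded subset of unknown size.

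A reader might infer that the rule will make Remodulin look safer than it is, or even reverse a real signal. One can build such a case: on-drug rates of 0.15 vs 0.10 per day, off-drug 0.10 in both arms, with 28 + 28 days on Remodulin and 14 + 28 on placebo. It gives (4.2 + 2.8)/28 = 0.25 against (1.4 + 2.8)/14 = 0.30, a ratio of 0.83 where the on-drug ratio is 1.5. But it rests on those same ceilings, and the documents do not establish the direction. The design assumes clinical worsening in 60% on placebo and 30% on Remodulin, so permitted unblinding might shorten placebo exposure more often. Earlier weaning on Remodulin would work the other way.

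**Conclusion.** The rule is wrong as written. Each arm's AE rate is overstated by 1 + hF/E whenever off-drug AEs occur. At E = 14 that is 1.0x, 1.1x or 1.5x under the none, low and middle assumptions. The 2.0x (E = 28) and 3.0x (E = 14) figures are ceilings, not expectations. All of these assume a constant hazard within the on-drug and off-drug periods.

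With no true difference, the arm comparison is distorted only if hF/E differs between arms. Protocol 6.2 makes that possible for unblinded subjects, but the size and direction are unknown. Dilution of a real on-drug difference is a separate consequence of counting off-drug AEs, and changing the denominator alone would not cure it.

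The effect is limited to one descriptive safety column. No inferential or efficacy result changes. It is worth correcting because the rate can create the kind of artefact that an exposure adjustment is meant to remove.

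**What to change.** Amend SAP 12.2, for the AE rate only:

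1. Count AEs with onset from first dose to last dose of study drug plus a short window stated in advance. Divide by the patient-days in exactly that period, ending it at discharge, death or withdrawal if earlier.
2. Keep subject counts and percentages for all TEAEs as planned.
3. State whether AEs and days on commercial Remodulin after Day 28 fall outside this rate, consistent with Day 28 being the last day of study drug. Without that statement, events to Day 56 can be counted with no days to match.
4. All TEAEs over all days from first dose to the end of AE recording may be shown as a supplement. It should not replace the rate in item 1, because it can mislead when off-drug hazard is lower and time on drug differs by arm.

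Matching the periods does not remove every difference: if hazard changes with time, arms observed for different lengths can still differ.

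The cost is one definition and one reprogrammed column. First-dose, last-dose and last-assessment dates are listed under SAP 9.1, and AE onset date and time are collected under Protocol 9.2. The end of AE recording is not a named date. It can be taken from the last assessment, since Protocol 7.3.4 places a "final assessment visit at the time of withdrawal from the study, hospital discharge, or at 4 weeks after discontinuing study drug", whichever is first, or from the death record.

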ⁿDocumentation of AEs will be recorded from the time informed consent is provided until subject is withdrawn from study, time of hospital discharge, or for 4 weeks after last dose of study drug, whichever comes first. All SAEs should be followed until resolution, death, or the subject is lost to follow-up, even if they are ongoing more than 4 weeks after completion of the subject’s last dose of study drug/final visit. If the subject receives Remodulin after hospital discharge, beyond Day 56/End of study, or following withdrawal from the study, AEs/SAEs will be subject to AE/SAE reporting under local government post-marketing AE/SAE reporting requirements.

^oApproximately every 6 hours (± 2 hours).

^pNot required for subjects unblinded and identified on placebo, or subjects continuing on Remodulin beyond Day 28.

^qIn the event that study drug is not discontinued (i.e., the subject continues on Remodulin beyond Day 28), the “Study Drug Discontinuation” and “48 Hour after Study Drug Discontinuation” assessments will not be collected. Follow-up/End of Study assessments will be performed.

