Subjects may continue on study drug for up to 28 days if clinically indicated. Per the investigator's discretion, if the subject is treated with Remodulin beyond Day 28, Day 28 will be considered as the last day of study drug administration. These subjects will continue to be followed in the study until they have reached Day 56 (4 weeks after last dose of study drug) or have been discharged from the hospital, whichever comes first.

6.1.4 *Dose Weaning*

Abrupt cessation of study drug will be avoided due to the risk of rebound pulmonary hypertension. Inhaled NO should be weaned and discontinued prior to initiating weaning of study drug. When the subject has reached the treatment goal and is ready to start weaning, the dose of study drug will be held constant at the same dose for at least 12 hours prior to initiating down titration. It is recommended the dose of study drug be decreased by no more than 10ng/kg/min per day either in the same incremental manner as the dose was increased or as determined by the Investigator. Dose decreases in increments greater than 5ng/kg/min are recommended to be avoided, but faster weaning may occur if required per subject care.

If withdrawal from study drug is warranted, the dose of study drug will be weaned until discontinued.

6.1.5 *Initiation of ECMO*

Subjects randomized to study drug may continue to receive study drug during ECMO at the pre-ECMO dose. Subjects should not be unblinded upon initiation of ECMO, unless required for purposes of medically managing the subject. At the conclusion of ECMO, weaning of study drug can begin per the Investigator's discretion.

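### The SAP's AE rate counts events after study drug stops but divides by study-drug days only, so it is too high in both arms, possibly by different amounts

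*SAP*

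**What the plan says.** SAP 12.2 puts a rate in every AE summary, next to the number and percentage of subjects and the number of events: "AE rate will be calculated as the total number of AEs divided by the total patient days of exposure to study drug per treatment group".

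Events summarised are the treatment-emergent ones: "Treatment-emergent adverse events (TEAEs) are those AEs with onset date equal to or after the start date of the study drug". The definition has a start but no end. The only AEs kept out of the summary tables are those before first dose.

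AE collection continues after study drug stops. Protocol 3.3.2.4 runs it to "time of hospital discharge, death, or until 4 weeks after the last dose of study drug, whichever comes first", with withdrawal and screen failure as further end points. Note n to Protocol Table 3-1 says the same ("time of hospital discharge, or for 4 weeks after last dose of study drug, whichever comes first"). Protocol 3.6 limits study drug to 28 days and total time in the study to 56 days.

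Protocol 6.2 governs time on drug after unblinding. If medical management requires it, treatment may be revealed at clinical worsening or after Day 14. For placebo, "Subjects randomized to placebo may be discontinued from study drug at that time", while Remodulin infants with unresolved disease may stay on study drug to Day 28. Infants moved to commercial Remodulin have Day 28 set as their last study-drug day but can be followed to Day 56 (Protocol 3.6, 9.3).

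**The concern.** A rate per patient-day needs events and days from the same window. Here the event window runs from first dose to the end of AE collection, and the day window ends at last dose. A reader will take the result as an on-drug rate, and it is not one.

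Two things follow. The level is too high in both arms whenever AEs occur after study drug stops. The size of the excess also depends on how long infants stay on drug, which Protocol 6.2 allows to differ by arm, so a between-arm difference in the rate can appear when none exists. Safety is part of the primary objective, and because no safety tests are planned (Protocol 10.3.3), readers depend on the descriptive figures.

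**Working it through.** The documents state no AE rate, expected exposure or expected follow-up, so there is no plan figure to reproduce.

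**Inputs.** From the documents: the numerator and denominator (SAP 12.2), the collection window (Protocol 3.3.2.4, Table 3-1 note n), the 28 + 28 day maximum (Protocol 3.6), and 60% and 30% worsening on placebo and Remodulin (SAP 5). Assumed: D = mean days on study drug, F = mean observed days after it, and the same constant AE hazard in both arms, so the true ratio is 1.00.

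**Level.** SAP rate ÷ rate on matched person-time = (D + F)/D.

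| D | F = 7 | F = 14 | F = 28 |
|---|---|---|---|
| 10 | 17/10 = 1.7 | 24/10 = 2.4 | 38/10 = 3.8 |
| 14 | 21/14 = 1.5 | 28/14 = 2.0 | 42/14 = 3.0 |
| 28 | 35/28 = 1.25 | 42/28 = 1.5 | 56/28 = 2.0 |

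F = 28 is a ceiling, since discharge, death or withdrawal ends collection sooner. If the off-drug hazard is r times the on-drug hazard, the excess over the on-drug rate is 1 + rF/D. For D = 14, F = 28 and r = 0.5 this is 2.0 instead of 3.0.

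**Between arms.** Take F = 28 and D = 10 unless a case says otherwise. Each arm's relative rate is (mean D + 28)/mean D, and the ratio is Remodulin/placebo.

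- *Half of worsened placebo infants (30% of the arm) stop on Day 3, no Remodulin infant does.* Placebo mean D = 0.3×3 + 0.7×10 = 7.9, rate 35.9/7.9 = 4.54. Remodulin 38/10 = 3.80. Ratio 0.84.
- *Half of worsened infants in both arms stop on Day 3 (30% and 15%).* Remodulin mean D = 0.15×3 + 0.85×10 = 8.95, rate 36.95/8.95 = 4.13. Placebo 4.54. Ratio 0.91.
- *Day 14 route alone, 10% of each arm with residual disease, placebo stopped at Day 14 and Remodulin continued to Day 28.* Remodulin mean D = 0.9×10 + 0.1×28 = 11.8, rate 39.8/11.8 = 3.37. Placebo mean D = 0.9×10 + 0.1×14 = 10.4, rate 38.4/10.4 = 3.69. Ratio 0.91. With 20%: (41.6/13.6)/(38.8/10.8) = 3.06/3.59 = 0.85.
- *Nobody stops early.* 1.00 if all have 10 drug days. If worsened infants in both arms stay on drug 14 days, Remodulin mean D = 0.3×14 + 0.7×10 = 11.2 and placebo 0.6×14 + 0.4×10 = 12.4, giving (39.2/11.2)/(40.4/12.4) = 3.50/3.26 = 1.07.

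AEs on commercial Remodulin after Day 28 count with no exposure days. This raises the Remodulin rate, which works against the ratios below 1.

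**Check of the two repairs when the off-drug hazard is half the on-drug hazard** (F = 28, placebo-only stopping on Day 3). Counting on-drug events over on-drug days gives 1.00. Dividing all treatment-emergent AEs by all observed days gives Remodulin (10 + 14)/38 = 0.632. Placebo is (5.8 + 14)/33.8 = 0.586 if all worsened infants stop (mean D = 0.6×3 + 0.4×10 = 5.8), a ratio of 1.08. If half stop, (7.9 + 14)/35.9 = 0.610, ratio 1.04. If a quarter stop, (8.95 + 14)/36.95 = 0.621, ratio 1.02.

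**The case against.** The strongest reply is that the consequence is small and its size unknown. Subject counts, percentages and event totals appear in the same tables and do not use this denominator. The SAP states the denominator openly, safety analysis is descriptive, and the listings hold the dates needed to recompute the rate. All of this stands, and it is why the point is minor.

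Constant hazard is also doubtful. Planned weaning starts only after oxygenation has improved and inhaled nitric oxide has stopped (Protocol 6.1.4), so infants who wean as planned are recovering, and the inflation would be smaller than the table shows. Infants who die contribute no days after drug, although the between-arm cases give every infant 28. This too stands.

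A reader might go further and infer that the rate will make Remodulin look much safer. If every worsened placebo infant stopped on Day 3 and no Remodulin infant did, the ratio would be 3.80/(33.8/5.8) = 3.80/5.83 = 0.65. The documents do not support that scenario. Stopping placebo is permitted, not required. Protocol 6.1.5 says "Subjects should not be unblinded upon initiation of ECMO, unless required for purposes of medically managing the subject", and Protocol 6.2 adds "All attempts should be made to maintain the blind during the study". Nor need Remodulin infants all continue: the example that Protocol 6.2 gives for unblinding is the start of another prostacyclin, when stopping Remodulin is plausible. If all worsened infants in both arms stopped on Day 3, the ratio would be 4.54/5.83 = 0.78.

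None of this removes the mismatch. Exposure-adjusted rates are standard practice, but they require the event window to match the exposure window, and nothing in either document limits the numerator to on-drug events or adds off-drug days to the denominator.

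**Conclusion.** The point holds as a minor correction. As written, the rate overstates the daily AE rate in both arms whenever AEs occur after study drug stops. The mismatch is plain in the text, and confidence in it is high.

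The size is not known. Inflation of 1.5 to 3.8 times for 10 to 14 drug days, and 2.0 times at the protocol maximum, rests on a constant hazard and assumed exposure and follow-up. The upper figures use the 28-day ceiling.

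Confidence in any between-arm bias is low. The cases run from 0.84 to 1.07 with no true difference, and commercial Remodulin use pushes the ratio upward. The documents support saying that the arms can be distorted unequally; they do not support saying which arm is favoured. Incidence comparisons are unaffected.

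**What to change.** Preferred, in SAP 12.2: keep study-drug days as the denominator, count only AEs with onset on study drug or within a short stated washout, and add the washout days to the denominator. State how Days 29 to 56 on commercial Remodulin are handled, either with both events and days counted or with both left out.

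Alternative: divide all treatment-emergent AEs by infant-days from first dose to the end of AE collection. This matches the windows, but the arm ratio is undistorted only if the hazard is the same on and off drug.

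Keep all planned treatment-emergent AE tables. The cost is one or two sentences and slightly more programming. AE onset is recorded with date and time (Protocol 9.2), and first-dose, last-dose and last-assessment dates are already listed (SAP 9.1). One limit: concomitant medications are recorded only to 48 hours after study drug stops, apart from those treating an AE (Protocol 4.3.1). The stop date of commercial Remodulin may therefore be missing, and leaving out both events and days after Day 28 is the simpler choice for the on-drug rate.
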